5.5. Missing Data

For continuous and categorical variables, data will not be imputed unless otherwise specified.

For safety analyses, any AEs with fully missing dates or partially missing dates, no date will be assigned. An AE will be considered treatment-emergent unless it can be unequivocally determined (from the partial onset date and/or a partial or complete stop date) that the event occurred prior to first dose of study drug.

For medications with partial start or stop dates, the first day/month will be imputed for start date, and the last day/month will be imputed for stop date. For medications with a completely missing start date, the medications will be considered as started prior to the first dose of study drug in this study; medications will be classified as prior or both prior and concomitant depending on the medication stop dates. If any medications have a completely missing stop date, then the medication will be assumed as ongoing.

5.6. Visit Windows

Data will be tabulated and analyzed per the visit as recorded on the electronic case report forms (eCRF) with the exception of visits prior to the first dose in this study [*Note: Protocol states any assessments performed in the parent study within 30 days before the first dose in Study 002 do not need to be recollected (except for vital signs and physical examination)*]. For any data that did not need to be recollected prior to the first dose in this study, the data at the latest visit from the parent study will be used for analysis.

Data at unscheduled visits will be included in by-patient listings and figures, but no assignment to a scheduled visit will be made for the purposes of by-visit summary tabulations. However, unscheduled visits will be considered for any categorical summaries (e.g., shifts from baseline to worst post-baseline value). For patients who discontinue study treatment, the time window for monitoring AEs and collecting PD assessments will be up to 84 days after the last dose.

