- Hatched columns indicate study visits to be conducted **only** for subjects who require monthly dosing.

^a Screening and Baseline visits may be combined, if possible. Assessments required prior to dosing during the screening or baseline visit in this protocol do not need to be repeated if performed in the ALN-GO1-001 protocol within the 30 days before the first dose with the exception of vital signs, ECGs, and physical examinations.

^b Patients who discontinue study drug early will be asked to return for their next scheduled visit to complete ET assessments and to complete safety follow-up visits once every 3 months, per the safety follow-up schedule in this table, for up to 6 months after the last dose of lumasiran (Section 5.3.1).

^c Demographic data will be obtained from Study ALN-GO1-001.

^d Complete medical history will be obtained at screening and any changes will be updated on admission at the Baseline visit, if different from the Screening visit. Events occurring after signing of the informed consent or assent (if applicable) form and before study drug administration will be captured as medical history.

^e During the Baseline visit and at EOT, height will be measured in triplicate for all patients; for all other study visits height will only be measured for patients <18 years of age. For patients <18 years of age, at each time point, height will be measured in centimeters, and in triplicate, to facilitate calculation of eGFR using the Schwartz Bedside formula.

^f Vital signs (blood pressure, heart rate, body temperature, and respiratory rate) will be measured in the supine or seated position after the patient has rested comfortably for approximately 10 minutes. Body temperature can be measured using oral, tympanic, or axillary methods; the temperature measurement method should be consistently utilized for the study duration, if feasible. At Baseline only, vital signs will be measured within 1 hour predose; and 30 minutes (\pm 5 minutes) and 4 hours (\pm 15 minutes) postdose.

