4. INVESTIGATIONAL PLAN

4.1. Summary of Study Design

This is a multicenter, open-label extension study to evaluate the long-term safety, PK, and PD of subcutaneously administered ALN-GO1 in patients with PH1 who completed Study ALN-GO1-001.

Consented eligible patients will enroll in this study and initially receive subcutaneous (SC) injections of ALN-GO1 at the same dose and regimen as they received in Study ALN-GO1-001. Based on emerging data, the SRC may authorize an alteration of dose and/or dose regimen to one that is no higher than the highest dose evaluated in either Part A or Part B of Study ALN-GO1-001. If such an authorization occurs, dose and/or dose regimen alteration may occur for an individual patient or entire cohort. This alteration may apply to subsequent doses for patients already enrolled and previously dosed in the study and/or to the initial dose and regimen for patients who have not yet been dosed in this study. Patients will be assessed for safety at each study visit.

PD assessments will be completed quarterly over the first 12 months on study, and approximately every 6 months thereafter for the study duration. PK assessments will be conducted during the first 12 months on study ([Table 1](#)).

Patients may receive ALN-GO1 as long as they do not fulfill any of the study discontinuation criteria (see [Section 5.3.1](#)) or until ALN-GO1 is commercially available in the patient's territory or the ALN-GO1 development program is discontinued (whichever comes first).

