4.2.1. Definition of the End of Study for an Individual Patient

The End of Treatment (EOT) visit is defined as the visit when the final dose of ALN-GO1 is administered. The End of Study (EOS) visit is defined as the visit 3 months after the EOT. Patients are considered to have completed the study when they have completed the EOS visit.

Patients who discontinue treatment but remain on study for assessments are considered to have reached the end of the study upon completing 6 months of monitoring following the final dose of ALN-GO1.

For patients who withdraw from the study, see [Section 5.3.2](#).

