8.2.8. Safety Analyses

Extent of exposure will be summarized. Adverse events will be summarized by the Medical Dictionary for Regulatory Activities (MedDRA) System Organ Class (SOC) and Preferred Term. Prior and concomitant medications will be classified using an internationally recognized and accepted coding dictionary.

Incidence of AEs (those events that started after exposure to study drug or worsened in severity after dosing) will be presented. Incidence of AEs will also be presented by maximum severity and relationship to study medication. The incidence of SAEs and AEs leading to discontinuation of treatment will also be tabulated. By-patient listings will be provided for deaths, SAEs, and events leading to discontinuation of treatment. Additional tabular summaries of AEs may be presented by other grouping including, but not limited to high level term (HLT), high level group term (HLGT), or standardized MedDRA query (SMQ).

Descriptive statistics will be provided for clinical laboratory data and vital signs data, presented as both actual values and changes from baseline relative to each on-study evaluation and to the last evaluation on study. Laboratory shift tables from baseline to worst values will be presented. Abnormal physical examination findings, renal ultrasound, ECG, and echo data will be presented in by-patient listings.

Descriptive statistics will be provided for electrocardiogram interval data and presented as both actual values and changes from baseline relative to each on-study evaluation and to the last evaluation on study. Details of any abnormalities will be included in patient listings.

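### SAP 5.6 tabulates by eCRF visit label with no study-day rule, so early-termination and early end-of-study values can be pooled into the Month 54 row

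*SAP*

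**What the plan says.** **Protocol**
- Table 1 has a single column, M54 (EOS/ET), at Day 1512 with a ±28-day window. The column before it is M51 (EOT), Day 1428. Safety follow-up after discontinuation has its own column, every 84 days.
- Table 1, footnote b: "Patients who discontinue study drug early will be asked to return for their next scheduled visit to complete ET assessments".
- Section 4.2.1: "The End of Treatment (EOT) visit is defined as the visit when the final dose of ALN-GO1 is administered", and "The End of Study (EOS) visit is defined as the visit 3 months after the EOT".
- Section 4.1 lets treatment continue "until ALN-GO1 is commercially available in the patient's territory or the ALN-GO1 development program is discontinued (whichever comes first".
- Section 8.2.8 promises, for laboratory, vital-sign and ECG interval data, "changes from baseline relative to each on-study evaluation and to the last evaluation on study".

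**SAP**
- Section 5.6: "Data will be tabulated and analyzed per the visit as recorded on the electronic case report forms (eCRF". The only exception is for visits before the first dose in this study.
- Section 5.6 on unscheduled visits: "no assignment to a scheduled visit will be made for the purposes of by-visit summary tabulations".
- Section 5.6 on patients who discontinue treatment: "the time window for monitoring AEs and collecting PD assessments will be up to 84 days after the last dose".
- The available SAP text has no rule for placing ET or EOS records.
- Sections 7.2.1, 7.2.2, 7.3.1 and 7.3.3 summarise the secondary and exploratory measures by scheduled visit. Section 5.4 splits tables and figures by initial dose regimen.
- Section 7.3.1 has no last-evaluation summary for laboratory, vital-sign or ECG data.

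**The concern.** Table 1 treats Month 54, EOS and ET as one visit, but the protocol's own definitions let ET and EOS fall at almost any time. Leaving before Month 54 is also foreseen by design, because treatment may end when the product becomes commercially available, at dates that differ by territory.

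Under a rule that follows the recorded label and ignores the study day, a value taken in the first year and one taken after more than four years can share a row. The Month 54 row is the last in each table and will be read as the long-term result. The early value would also be absent from the row for the month in which it was collected. With at most 20 patients split by regimen, a few such values could move a mean visibly.

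SAP 5.7 adds a further exposure. It plans interim analyses for regulatory use and publication. Under a shared label, a cut-off before anyone reaches Month 54 would produce a Month 54 row made up only of early leavers.

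**Working it through.** **1. Schedule.** In 28-day months, 54 × 28 = 1512 and 51 × 28 = 1428, which matches Table 1. The gap is 84 days. EOS therefore coincides with Month 54 only for a patient whose last dose is at Month 51. For anyone else who leaves, EOS or ET comes earlier.

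**2. What SAP 5.6 does under each possible eCRF design.** The eCRF is not among the documents.

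| How the eCRF labels the record | Effect on the Month 54 row | Effect on the row for the month of collection |
|---|---|---|
| One label for M54, EOS and ET, as Table 1 is drawn | Early values are included | Early value is missing |
| Separate ET or EOS labels | None | Early value is missing; the SAP does not say where it is shown |
| Site records the nominal month of the next scheduled visit | None | Value is in the right row |

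No passage says which design applies.

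**3. Size under a shared label (illustration).** N = 20 is the planned maximum (protocol 4.3), and Day 1512 is from Table 1. The number of leavers k, their ET day d and a common linear eGFR slope s are assumptions; the documents give none of them. All 20 are taken to contribute a value.

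Shift in mean change = (k/N) × |s| × (1512 − d)/365.25

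- Central case, k = 4, s = −3 mL/min/1.73 m² per year, d = 337: (4/20) × 3 × 1175/365.25 = 1.93. The change that each such leaver's value omits is 3 × 1175/365.25 = 9.65.
- Low end, k = 2, s = −1, d = 673: (2/20) × 1 × 839/365.25 = 0.23.
- High end, k = 6, s = −5, d = 169: (6/20) × 5 × 1343/365.25 = 5.52.
- By regimen, in an assumed group of 6 with one leaver at d = 337 and s = −3: (1/6) × 3 × 1175/365.25 = 1.61.

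With a declining eGFR, the shift makes Month 54 look better than it is.

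**4. The same point without a slope.** Mean elapsed time in the row = ((20 − k) × 54 + k × m)/20, where m is the leavers' mean month. With k = 4 it is 50.4, 48.0 and 45.6 months for m = 36, 24 and 12. With k = 0 it is 54.0.

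**5. Would study-day windows place every record?** No. Take a last dose at Month 18 (18 × 28 = Day 504). EOS is then at Day 504 + 84 = 588. The ±28-day windows end at Day 532 for Month 18 and start at Day 644 for Month 24 (24 × 28 = 672), so Day 588 lies in neither. A separate ET/EOS row is needed as well.

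**6. The 84-day PD limit.** After Month 12, scheduled visits are 168 days apart with a ±28-day window, so ET can fall up to 168 + 28 = 196 days after the last dose. The limit may therefore remove some ET samples from the PD summaries. It does not assign the remaining ones to a visit.

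**The case against.** The strongest reply is that a column in a schedule of assessments shows only that the same procedures apply; it does not define an eCRF label. That stands. A reader might infer that early leavers' values are in fact averaged into Month 54, and the documents do not support this. Footnote b sends the patient to the next scheduled visit, so a site may well record that month, and a separate ET label would also keep Month 54 clean.

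Other points that stand:
- A reader might infer that earlier rows would describe continuing patients only. They would not. A patient with ET at Month 9 still contributes to every row before Month 9; at worst one row loses a value.
- A reader might infer that the SAP dropped a promised last-evaluation summary for oxalate and eGFR. Protocol 8.2.8 promises it only for laboratory, vital-sign and ECG data, and protocol 8.2.5 promises none for PD or eGFR. SAP Section 8, which lists changes to planned analyses, was not available, so an unexplained omission cannot be asserted.
- The SAP seems to follow an earlier protocol version. It keeps quality of life as an endpoint, lists renal ultrasound only to Month 24 and never names Month 54.
- All analyses are descriptive, and the number of observations is reported with each summary.

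None of this supplies a placement rule. Section 5.6 does state a rule, to follow the recorded label, and it holds back only unscheduled visits from the by-visit tables. Whether early values reach Month 54 is then left to eCRF design and site practice.

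**Conclusion.** The point holds as a risk that the stated rule leaves open. If the eCRF follows Table 1, values from patients who leave early can be pooled into the Month 54 row of the by-visit summaries and mean plots, and be missing from the row for the month of collection.

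The size cannot be derived from the documents. It is zero with separate labels or nominal-month recording. With a shared label it is about 1.9 mL/min/1.73 m² for eGFR in the central case (range 0.23 to 5.52 over the inputs tried), but the slope, the number of leavers and the ET day are all assumed. These figures should not be read as an estimate of bias in this trial.

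AE incidence (the primary endpoint), worst-value shift tables, listings and the interpolated percentage-of-time analysis do not depend on the Month 54 label. The eGFR slope model is also unaffected if it uses actual time, which SAP 7.2.2 does not state.

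**What to change.** In SAP 5.6:
1. Admit to the Month 54 row only records within Day 1512 ±28.
2. Assign ET and early EOS records to the scheduled visit whose window contains their actual study day. For PD, apply this within the existing limit of 84 days after the last dose.
3. Show any ET or EOS record that falls in no window in a separate ET/EOS row.
4. Flag off-treatment values, so that mapping by day does not mix them unmarked with on-treatment values.

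In SAP 7.3.1, include the last-evaluation summary from protocol 8.2.8 for laboratory, vital-sign and ECG data, unless SAP Section 8 already explains its removal.

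The cost is SAP wording and a small amount of visit-mapping programming before database lock. No new data are needed.

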5.7. Interim Analysis

Interim analyses will be performed to support regulatory activities and publications. These analyses will be descriptive in nature and will not involve any formal hypothesis testing.

For interim analyses, as this study will be ongoing, a cut-off approach will be implemented to ensure data quality. The interim analysis will include data entered on or prior to a pre-specified cutoff date. For assessments with start or end dates (e.g., exposure, AEs, medical history, etc), the start date will be compared to the prespecified cutoff date to determine whether the assessment is included in the analysis.

6. STUDY ANALYSES

6.1. Patient Disposition

Number and percentage of patients will be tabulated for the following categories:

- Enrolled (signed informed consent and met eligibility)
- Safety Analysis Set
- PD Analysis Set
- PK Analysis Set

Summaries of the number and percentage of patients who discontinued treatment based upon the primary reason for discontinuation (e.g., AE, death, lost to follow-up, etc) will be presented.

Summaries of the number and percent of patients who withdrew from the study prematurely and the associated reasons for withdrawal will be presented. Per patient data listings will be presented displaying the primary reason that the patient discontinued treatment and/or went off study.

6.2. Demographics and Baseline characteristics

Baseline characteristics will be based upon the derived baseline in Study ALN-GO1-001 (refer to ALN-GO1-001 SAP; dated August 13, 2018). These characteristics include but are not limited to age, gender, race, ethnicity, body weight, body height as well as baseline 24-hour urinary oxalate excretion corrected for body surface area (BSA), 24-urinary oxalate: creatinine ratio and eGFR. For a subset of baseline parameters (e.g. Quality of Life, renal ultrasounds, etc..), the baseline will be based upon the first dose of lumasiran in this study.

6.3. Medical History

Data recorded in medical history in this study and in the parent study (ALN-GO1-001) will be summarized by Medical Dictionary for Regulatory Activities (MedDRA) system organ class (SOC), high level term (HLT) and preferred term (PT). A patient will only contribute once to the count for a given condition (overall, by SOC, by HLT, by PT). Medical history and pregnancy test results will also be presented in data listings.

6.4. Concomitant Medications

Concomitant medications are defined as medications which were taken after the first dose date of the study drug in this study and any medication that started prior to the first dose in this study and was ongoing on or after the date of the first dose of study drug in this study.

Tabular summary of the number and percentage of patients taking concomitant medications will be summarized by anatomic therapeutic class (ATC) and PT. Data will be presented for the Safety Analysis Set. A separate tabular summary of concomitant vitamin B6 use will be summarized by ATC and PT.

By-patient listings will be generated separately for concomitant medications and vitamin B6 medications.

6.5. Dosing and Extent of Exposure

Summaries of exposure will include the following categories such as, but not limited to: total number of doses received per patient, mean number of doses per patient, cumulative number of doses received per study group, duration of drug exposure (months) per study group, cumulative drug exposure time (months) per study group, the total dose administered (mg) and total volume administered (mL).

Definition of drug exposure (days) will be defined as the minimum of [Exposure time= (date of last exposure – date of first dose +1)] where date of last exposure will represent either the date of the last dose administered dose +84, analysis cut-off date or end of study date.

Dose interruptions and compliance are not taken into account.

A separate per-patient exposure listing will be generated to display the initial dosing regimen in the parent study (ALN-GO1-001), the initial dosing regimen in this study and changes to the dose and/or regimen during this study.

7. STATISTICAL ANALYSIS

7.1. Primary Endpoint

7.1.1. Evaluate the incidence of Adverse Events (AEs)

The primary safety parameter is the assessment of treatment-emergent AEs which will be defined as an AE that occurs or worsens on or after the first lumasiran dose date/time of this study though 84 days after the last dose of study drug. In addition, any AE that worsens in intensity or was subsequently considered related to study drug will be considered treatment-emergent. All analyses of AEs will be performed on the Safety Analysis Set.

For summaries of AEs, there will be 3 sets of summaries: all AEs, AEs classified as renal stone events and AEs excluding those classified as renal stone events. A medical review of all AEs will be conducted to identify renal stone events.

AEs will be coded using the MedDRA coding system (version 21.0 or later) and displayed in tables and data listings by SOC and PT. Patients who report multiple occurrences of the same PT will be classified according to the most related or most severe category. Patients with a missing relationship to study drug will be classified as the most related category. Drug related AEs include events considered definitely related or possibly related to study drug by the investigator or events with missing relationship.

An overview table of AEs will be tabulated. The overview table will include the number and percentage of patients in following categories such as, but not limited to:

- At least 1 AE
 - At least 1 drug related AE
- At least 1 severe AE
 - At least 1 drug related severe AE
- At least 1 serious adverse event (SAE)
 - At least 1 drug related SAE
- At least 1 AE leading to treatment discontinuation
 - At least 1 drug related AE leading to treatment discontinuation
- At least 1 AE leading to study withdrawal
 - At least 1 drug related AE leading to study withdrawal
- Death

Tabulations by SOC and PT displaying the number of patients (percentage) and total events will be produced for the following tables:

- All AEs
- Serious AEs
- AEs by maximum severity

- AEs related to treatment
- AEs and SAEs related to treatment by maximum severity

There will also be an all AE table generated displaying rates of AEs adjusted for exposure-time.

Separate listings will be provided for deaths, SAEs, and AEs leading to discontinuation of study drug, dose interruption, or study withdrawal. By-patient AE listings will be provided.

A subset of key AE outputs will also be generated to compare study groups of patients initially dosed with 3 mg/kg once monthly versus 3 mg/kg once every 3 months of lumasiran.

Tabulations of the AE data will be adjusted for exposure-time.

Summaries of other Standardised MedDRA Queries (SMQs) or AE groupings may be summarized such as but not limited to the following:

Injection Site Reactions [ISRs]: AEs mapping to the HLT="Injection Site Reactions" using MedDRA dictionary will be included in the summary. Frequency (percentages) of ISRs by HLT and PT will be generated. A separate listing will be generated to display all patients who reported ISRs.

A table will also be generated to display the number of patients with at least 1 ISR, total number of injections, total number of injections complicated by ISRs and corresponding % of injections complicated by ISR with the most common signs and symptoms reported due to ISRs. If there are multiple ISRs that occur in between 2 consecutive injections, then these events will be considered as 1 ISR and considered related to the preceding injection.

Hepatic AEs, including AEs of liver function test (LFT) abnormalities: AEs mapping to the SMQ drug-related hepatic disorders - comprehensive search (includes all narrow and broad terms). Frequency (percentages) of drug-related hepatic disorders will be summarized by SOC and PT. A separate listing will be generated of all patients reporting these events.

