5.3.1. Discontinuation of Study Drug

The Investigator or designee may discontinue dosing in a patient if the patient:

- Is in violation of the protocol
- Experiences a serious or intolerable AE
- Becomes pregnant
- Is found to be considerably noncompliant with the protocol requirements

The Investigator will confer with the Sponsor or Medical Monitor before discontinuing dosing in the patient. Patients who are pregnant will be discontinued from dosing immediately (see Section [7.4.8.6](#) for reporting and follow-up of pregnancy). In general, patients who discontinue study drug dosing for any reason will be encouraged to complete the End of Treatment assessments and safety and PD follow up visits so that their experience is captured in the final analyses. Patients who discontinue study drug but who remain on study may receive local standard of care treatment for their disease, as applicable.

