7.4.8.2. Eliciting and Recording Adverse Events

Eliciting Adverse Events

The patient should be asked about medically relevant changes in his/her health since the last visit. The patient should also be asked if he/she has been hospitalized, had any accidents, used any new medications, or changed concomitant medication routines (both prescription and over-the-counter). In addition to patient observations, AEs will be documented from any clinically relevant laboratory findings, physical examination findings, electrocardiogram changes, or other findings that are relevant to patient safety.

Recording Adverse Events

The Investigator is responsible for recording non-serious AEs that are observed or reported by the patient after administration of the first dose of study drug regardless of their relationship to study drug through the end of study. Non-serious AEs will be followed until the end of study.

The Investigator is responsible for recording SAEs that are observed or reported by the patient after the time when the informed consent is signed regardless of their relationship to study drug through the end of study. SAEs will be followed until satisfactory resolution, until baseline level is reached, or until the SAE is considered by the Investigator to be chronic or the patient is stable, as appropriate.

All AEs must be recorded in the source records for the clinical study center and in the eCRF for the patient, whether or not they are considered to be drug-related. Each AE must be described in detail: onset time and date, description of event, severity, relationship to investigational drug, action taken, and outcome (including time and date of resolution, if applicable).

For SAEs, record the event(s) in the eCRF. If the electronic data capture (EDC) system is unavailable, complete the back-up SAE form.

For AEs that are considered AEs of clinical interest, additional clinical information may be collected based upon the severity or nature of the event. Refer to CRF completion guidelines for details on reporting events in the supplemental eCRF.

For all ISRs, the Investigator, or delegate, should submit an Injection Site Reactions Signs or Symptoms eCRF, recording additional information (eg, descriptions, onset and resolution date, severity, treatment given, and event outcome).

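### For patients who stop drug but stay on study, the SAP ends AE counting and PD collection 84 days after the last dose, while the protocol follows them for up to 6 months

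*SAP*

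**What the plan says.** **SAP.** Section 7.1.1 takes the treatment-emergent AE as the primary safety parameter. An event qualifies if it "occurs or worsens on or after the first lumasiran dose date/time of this study though 84 days after the last dose of study drug". The section adds that "any AE that worsens in intensity or was subsequently considered related to study drug will be considered treatment-emergent" and gives no time limit for that clause. Section 5.6 states, for patients who discontinue treatment, that "the time window for monitoring AEs and collecting PD assessments will be up to 84 days after the last dose". Section 6.5 stops exposure time at the earliest of last dose plus 84 days, the analysis cut-off and the end of study.

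**Protocol, same patients.** Table 1, footnote b asks patients who stop drug early to attend safety visits every 3 months "for up to 6 months after the last dose of lumasiran". Section 4.2.1 says that those who stop drug but stay on study "are considered to have reached the end of the study upon completing 6 months of monitoring following the final dose of ALN-GO1". Section 7.4.8.2 has the investigator record AEs and SAEs "regardless of their relationship to study drug through the end of study". Section 5.3.1 encourages these patients to complete "safety and PD follow up visits so that their experience is captured in the final analyses". Section 8.2.8 describes the AEs whose incidence is presented as "those events that started after exposure to study drug or worsened in severity after dosing", with no end date.

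**The concern.** The two documents give different periods for one group of patients, on the primary endpoint. A completer's nominal follow-up after the last dose is 84 days, so the SAP window covers it. A patient who stops drug but stays on study may be followed for about twice as long. Under the SAP, a new unrelated SAE at, say, day 100 after the last dose would be collected and listed but would enter no incidence table.

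Two further points follow from the same wording.

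- **PD.** The sentence in SAP 5.6 also limits PD collection, although protocol 5.3.1 speaks of PD as well as safety follow-up visits.
- **Exposure-adjusted rates.** If the clause on worsening or later-related AEs reaches past day 84, those AEs would be counted with no matching person-time, because exposure stops at last dose plus 84 days.

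**Working it through.** The plan states no figure to reproduce: the sample size has no power calculation, and neither document gives an expected number of discontinuers. The check is day arithmetic, followed by an illustration on labelled assumptions.

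**1. Completers (protocol Table 1).** EOT is day 1428 and EOS day 1512. 1512 − 1428 = 84 days, so the SAP window fits them.

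**2. Patients who stop drug and stay on study.** The gap is protocol follow-up minus 84 days.

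| Reading of 6 months | Follow-up (days) | Outside the window (days) | Share |
|---|---|---|---|
| Two 84-day intervals | 168 | 168 − 84 = 84 | 50% |
| Calendar months, 365.25/2 | 182.6 | 182.6 − 84 = 98.6 | 54% |
| 168 days plus the 28-day visit window | 196 | 196 − 84 = 112 | 57% |

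The lower limit is 0, because the protocol's period is a maximum and the visits are only requested.

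**3. Share of study follow-up.** Assume that k of 20 patients stop with the last dose on study day D and are followed to D + 168, and that the others are followed for 1512 days.

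Share = 84k / [(20 − k) × 1512 + k × (D + 168)]

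| D | k = 1 | k = 5 |
|---|---|---|
| 1 | 84/28,897 = 0.29% | 420/23,525 = 1.79% |
| 714 | 84/29,610 = 0.28% | 420/27,090 = 1.55% |
| 1344 | 84/30,240 = 0.28% | 420/30,240 = 1.39% |

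If no discontinuer stays past day 84, the share is 0. The range is therefore 0% to 1.8%.

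**4. Chance of at least one untabulated SAE.** Assume a Poisson rate of r unrelated SAEs per patient-year and full 6-month follow-up. Each gap is 84/365.25 = 0.230 patient-years.

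P = 1 − exp(−0.230 × k × r)

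- k = 1, r = 0.1: 2.3%
- k = 3, r = 0.25: 15.8%
- k = 5, r = 0.5: 43.7%

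**5. Chance that SAE incidence changes.** This needs a patient with an SAE in the gap and none between first dose and last dose plus 84 days. Per patient, with r = 0.5:

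p = exp(−0.5 × (D + 84)/365.25) × [1 − exp(−0.5 × 84/365.25)]

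The second factor is 0.109. For five such patients the chance is 1 − (1 − p)^5.

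- D = 1: p = 0.890 × 0.109 = 0.097, chance about 40%
- D = 714: p = 0.335 × 0.109 = 0.036, chance about 17%
- D = 1344: p = 0.142 × 0.109 = 0.015, chance about 7.5%

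These use the highest values assumed here for both k and r. One affected patient of 20 moves incidence by 1/20 = 5 percentage points.

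**The case against.** **The 84-day window is a sound choice.** A reader might infer that the treatment-emergent definition is itself wrong. The documents do not support that. The window matches the completers' interval from EOT to EOS and the exposure cap in SAP 6.5, so numerator and person-time agree. This objection stands, and the window should stay.

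**The SAP may add detail.** Protocol 8.2 says its statistical section summarises fuller plans to be given in the SAP, and 8.2.8 is silent on an end date rather than explicit that none applies. That is fair as regards SAP 7.1.1. It does not explain SAP 5.6, which gives a monitoring period shorter than the protocol's for the same patients.

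**The difference may be declared or out of date.** A reader might infer an undeclared departure from the protocol. That cannot be shown. SAP 1 places changes and their justification in Section 8, whose text was not available for this review. The SAP also seems to follow an older protocol: it keeps a quality-of-life objective that the protocol has dropped, and it describes renal ultrasound only to Month 24. This lowers the weight of the point, but the texts still need to agree.

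**Late events are not lost.** A reader might infer that they vanish from the report. They do not. SAP 7.1.1 plans listings of deaths and SAEs and by-patient AE listings, with no 84-day limit stated, and with at most 20 patients these are readable. Some late events may also be tabulated: AEs with missing relationship are classed as most related, and under SAP 5.5 incompletely dated AEs count as treatment-emergent unless they clearly preceded the first dose. What remains is that listed events have no incidence summary and no person-time.

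**Conclusion.** The point holds and is minor. The 84-day limit in SAP 5.6 and 7.1.1 does not agree with the follow-up period in protocol 4.2.1 and Table 1, footnote b. As written, new-onset AEs and SAEs that start after day 84 and are not considered related would be listed but not tabulated.

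Per discontinuer who stays on study, 0 to about 84 of 168 post-dose days are affected on the nominal schedule, or about 99 days by calendar months. Study-wide the share is 0% to 1.8% if up to 5 of 20 patients stop. The number of discontinuers is not in the documents, so the effect is probably small and may be zero.

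A reader might take the 43.7% as the chance that reported SAE incidence is wrong. It is not. It is the extreme corner of the assumptions, and it is the chance of any untabulated SAE. The chance that incidence changes is about 40%, 17% or 7.5% on those same extreme assumptions, depending on when patients stop. All of these rest on assumed rates and numbers, and none is a forecast.

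**What to change.** 1. Reconcile the window in SAP 5.6 with protocol 4.2.1 and Table 1, footnote b. Do so for PD as well as AEs, since one sentence governs both.
2. Keep the 84-day treatment-emergent tables and the exposure-adjusted rates unchanged.
3. Add one table or column of AEs, SAEs and deaths with onset after day 84 through the patient's end of study, regardless of relationship, with its own person-time.
4. Keep any late AE brought in by the clause on worsening or later-related events out of the rates whose person-time stops at last dose plus 84 days.

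The cost is some SAP wording and one small extra output from data that the protocol already collects. Late off-drug events would be shown separately, and the existing incidence figures would not change.
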